**Pilot Test of a Substance Use Treatment and Recovery Team (START)
for Medical Inpatients with Opioid and Alcohol Use Disorders**

Version 3.1 08APRIL2021

Principal Investigators:
[name] (RAND)
[name] (Cedars-Sinai)

Cedars-Sinai Medical Center
NCT04314648

TABLE OF CONTENTS

PROTOCOL SUMMARY	3
GENERAL INFORMATION	3
1.0 BACKGROUND, RATIONALE.....	3
2.0 STUDY OBJECTIVES.....	4
3.0 STUDY POPULATION	4
3.1 SELECTION OF THE STUDY POPULATION	4
3.2 INCLUSION CRITERIA	5
3.3 EXCLUSION CRITERIA.....	5
3.4 SUBJECT SCREENING AND ENROLLMENT	5
3.5 SUBJECT RECRUITMENT	5
4.0 STUDY DESIGN AND METHODS.....	7
5.0 DATA COLLECTION AND MANAGEMENT	12
5.1 DATA PROCUREMENT	12
5.2 TIME PERIOD OF DATA UNDER REVIEW	12
5.3 VARIABLES COLLECTED	12
5.4 SOURCE DOCUMENTS.....	15
5.5 DATA COLLECTION AND STORAGE.....	15
5.6 CONFIDENTIALITY AND SECURITY OF DATA.....	15
6.0 DATA AND SAFETY MONITORING	16
6.1 DATA AND SAFETY MONITORING PLAN.....	16
6.2 QUALITY CONTROL AND QUALITY ASSURANCE	19
7.0 STATISTICAL CONSIDERATIONS.....	19
7.1 STUDY OUTCOME MEASURES.....	19
7.2 SAMPLE SIZE CONSIDERATIONS	19
8.0 APPENDICES	20
9.0 REFERENCES	22

PROTOCOL SUMMARY

Purpose and Knowledge to be Gained	
 The purpose the research is to conduct a pilot test of a substance use treatment and recovery team (START) for medical inpatients with opioid and alcohol use disorders If the aims of the research are achieved, we hope to improve Medication-Assisted-Treatment (MAT) initiation and linkage to follow-up care and clinical outcomes, and, ultimately, reduce 90-day readmission rates for inpatients with OAUDs
Research Procedures	
The primary research procedures are
 
 Baseline interview with patient 1-month follow-up interview with patient Provider interviews
Subject Population	
 Inpatients at CSMC 18 or older who screen positive for moderate to severe OAUDs
Duration	
 The study includes 2 visits (Baseline interview, 1-month follow-up interview). The total study duration is 1 month

GENERAL INFORMATION

CSMC Co-Investigators	[name] [name] [name] [name] Responsibilities include consenting of subjects and delivery of intervention.
Sponsor/Funder	NIDA (National Institute on Drug Abuse)

1.0 BACKGROUND, RATIONALE

- There is a large unmet need for substance-use disorder (SUD) treatment in the U.S. In 2015, 20.4 million adults in the U.S. (8.4 % of all adults) needed treatment for an illicit drug or alcohol use problem; of these, 18.1 million did not receive it.¹ The consequences of untreated SUDs are enormous: premature death, billions of dollars in avoidable health care and criminal justice costs, decreased economic productivity, individual suffering, and long-term harmful effects on families and communities.²⁻⁶ Opioid and alcohol use disorders (OAUDs) are of particular concern because of high rates of morbidity, mortality, hospitalizations and readmissions,⁷⁻¹⁰ and because of the increasing incidence of opioid-use disorders (OUD) and associated consequences from the non-medical use of prescription opioids.¹¹ Medication-Assisted-Treatment (MAT) is available for OAUDs, but less than a quarter of publicly funded treatment programs¹² and fewer than half of private sector treatment programs offer MAT.
- Despite high prevalence, few inpatients with OAUDs receive evidence-based treatments while in the hospital.¹³⁻¹⁵ Most physicians and other providers in acute hospital settings are not trained to assess or manage patients with OAUDs,¹⁶ contributing to low rates of OAUD identification

and treatment initiation.¹⁷⁻²¹ Pharmacotherapies to address AUDs (acamprosate, oral and injectable naltrexone, and disulfiram) and OUDs (buprenorphine/naloxone, methadone, and oral and injectable naltrexone) are effective for use across medical settings²²⁻²⁸ but are seldom administered in hospitals or recommended as part of follow-up care.^{29,30} New research demonstrates that initiating buprenorphine/naloxone in the emergency department with follow-up in primary care for patients with OUDs can increase SUD treatment entry and abstinence,³¹ and that inpatients with complications from OUDs are amenable to initiating medication in the hospital and being linked with follow-up care.³² The current standard of care for hospitalized patients with OAUDs is screening, brief intervention outcomes for people with moderate to severe AUDs or for people with OUDs.^{33,34,16,35} Two possible reasons are that SBIRT does not incorporate MAT initiation or address the needs of those needing more than a brief intervention prior to referral. Barriers to initiating MAT for hospitalized patients may include lack of OAUD treatment expertise on the medical team and absence of a patient-centered, measurement- and population-based system for assessing and treating patients with OAUDs. Embedding a collaborative care team (START) for inpatients with OAUDs within an existing hospital consultation-liaison psychiatry service could improve MAT initiation and linkage to follow-up care and clinical outcomes, and, ultimately, reduce 90-day readmission rates.

- Collaborative care is a systematic approach to organizing and coordinating care for patients with complex conditions.³⁶ Based on the Chronic Care Model developed by Wagner et al.,³⁷ collaborative care addresses barriers to assessing and providing comprehensive, patient-centered care and leads to improved care and patient outcomes.^{38,39} Collaborative care has four core attributes: (1) Team-driven: a behavioral health team is integrated into the medical team to provide coordinated care and develop patient-centered care plans; (2) Population-focused: the team provides care to a defined group of patients; (3) Measurement-based: The team of 12 uses systematic, patient-reported measures to drive clinical decision-making; and (4) Evidence-based: the team facilitates use of evidence-based practices in the clinical setting.⁴⁰⁻⁴³ Collaborative care approaches have enhanced integration of specialized care for depression and other chronic diseases into busy medical practices where providers do not have time or expertise to fully assess or manage care for patients with complex chronic conditions,³⁶ but they have not been tested for OAUDs in the inpatient setting. Moreover, recent research on the experience of medical inpatients identified with SUDs suggests the importance of access to MAT while in the hospital and coordinated care post-discharge.⁴⁴

2.0 STUDY OBJECTIVES

Primary Objectives:

Test if embedding a collaborative care team called START the substance use treatment and recovery team (START) for inpatients with OAUDs within an existing hospital consultation-liaison psychiatry service could improve MAT initiation and linkage to follow-up care and clinical outcomes, and, ultimately, reduce 90-day readmission rates.

Secondary Objective:

In a larger study, subsequent to the pilot, we will test 90-day readmission rates and whether lower readmission rates are mediated by MAT initiation and linkage to follow-up care.

3.0 STUDY POPULATION

3.1 SELECTION OF THE STUDY POPULATION

CSMC inpatient population. Approximately 80 patients will be enrolled over the course of 5 months. Additionally, we will conduct semi-structured in-person or remote (telephone or

video) interviews with up to 10 physicians, 10 nurses, and 10 social workers from within the hospital who treat START patients during the pilot period, as well as up to 10 telephone interviews with follow-up providers who received patients referred from the hospital during the pilot period.

3.2 INCLUSION CRITERIA

1. Inpatient at CSMC
2. Age 18 and older
3. Screens positive for moderate to severe OAUDs based on the alcohol and opioid questions on the World Health Organization (WHO) Alcohol, Smoking, and Substance Involvement Screening test (ASSIST).⁴⁵ Patients with scores >10 for alcohol or >3 for opioid use will be eligible for the study
4. Speaks English as primary language
5. Willing to participate in, and able to provide contact information for, telephone follow-up calls and follow-up interview
6. Able to provide informed consent

3.3 EXCLUSION CRITERIA

1. Currently receiving FDA-approved medication treatment for an opioid or alcohol use disorder
2. Life expectancy of <6 months

3.4 SUBJECT SCREENING AND ENROLLMENT

- Data for screening will be procured using a daily data extract of potentially eligible subjects (variables include demographics, alcohol and/or opioid history and screenings).
- The Principal Investigator, Co-Investigators, and approved study staff will have access to these records.

3.5 SUBJECT RECRUITMENT

[figure not shown]
The study will recruit adults with moderate to severe OAUDs who are admitted to the inpatient medical center. Patients will be identified through physician referral, or through review of an existing daily EPIC workbench report of opioid and alcohol misuse (Daily Report). The approved CSMC study staff will identify patients with probable moderate-to-severe OAUD through a daily printout from EPIC or by direct provider referrals from physicians and social workers (see Figure 1 below).

- The CSMC approved study staff will identify patients with probable moderate-to-severe OAUD through a Daily Report or by direct provider Medical Staff referrals.
- Once a potential patient is identified, someone from the study team will contact the attending physician, briefly explain the study, and ask the physician for permission to contact the patient.
- If the attending physician agrees, the physician or someone from the medical team will explain the study to the patient and ask for their permission to be visited by study staff.
- Advertising and recruitment materials:
For providers:
 - Study Physician Flyer
 - Physician Screening Card
 - Physician Recruitment Letter

For patients:

- Physician to Patient Letter (Dear Patient Letter) to be provided by the treating physicians to patients deemed eligible for the study.

Figure 1: Recruitment, Enrollment, and Randomization Diagram

4.0 STUDY DESIGN AND METHODS

- Eligibility screening - Assessments, demographics (conducted in person or remotely)
- Informed Consent, if eligible (to be obtained in person either on paper or electronically using an approved platform or remotely using an approved platform)
- Enrollment - the CSMC study staff will enroll consented, eligible patients.
- Baseline interview - after enrollment, the CSMC approved study staff will conduct an in-person or remote 30-40-minute baseline interview. Interview data will be recorded on a tablet or computer into a web-based survey system (REDCap). Patients will be compensated with a \$50 Forte payment card (given in person or mailed).
- Randomization - following consent and the baseline interview, the CSMC approved study staff will randomize the patient to the START or UC arm using REDCap.
- All patients will be given patient education materials on alcohol and/or opioid use disorder, as well as harm reduction materials (OUD only). If the visit is remote, the research team will give these materials to a member of the medical team to deliver to the patient or place them in the patient's room.
- 1-month post discharge follow-up interview - the CSMC approved study staff will conduct a follow-up interview by telephone 1-month after the patient is discharged from the hospital. Patients will receive \$50 loaded onto their existing Forte payment card for participation.

The components of the START workflow process are as follows (also shown in Figure 2):

[figure not shown]
1. Triage (Care Manager CM and Addiction Medicine Specialist AMS):
The CM assesses the patient for acute biomedical needs related to the OAUD. The AMS addresses acute biomedical needs (e.g. facilitates withdrawal management).
2. Engage, assess, plan (CM and AMS) (conducted in person or remotely based on circumstances):
3. If there is not an urgent need for medical intervention or after the urgent medical need is addressed, the CM and/or AMS:
 - engages with the patient (CM and AMS)
 - conducts a diagnostic and biopsychosocial assessment (CM)
 - conducts a complete biomedical assessment and addresses comorbidities (AMS)
 - delivers the brief negotiated interview (BNI), an evidence-based intervention, to assess to increase readiness and develops a plan for initiating evidence-based treatment for OAUD (MAT) and/or psychosocial treatment) during and after the hospital stay (CM)
 - ensures the patient understands the follow-up plan and addresses barriers (CM).
4. Treat (AMS) The AMS:
 - facilitates MAT initiation
 - facilitates psychosocial treatment for the substance use disorder, if indicated and available.
5. Communicate and Coordinate (CM, AMS)
 - The CM and AMS communicate with each other to continue care through one-month (or more) after the patient is discharged.
 - The CM and AMS communicate with the patient and medical team, and, when appropriate, the patient's family and outpatient providers.
6. Follow-up (CM):

- The CM calls the patient once a week for 1 month after the patient is discharged from the hospital to assess whether the patient is following through with the discharge plan.
- The CM may also call outpatient providers to determine if the patient linked to care and has encountered barriers.

7. Monitor (AMS):

- The AMS continues to monitor the patient after discharge through the CM's follow-up work.

Figure 2: START Workflow Diagram

INNOVATION

- This proposed study identifies the inpatient hospital stay as a new opportunity to initiate MAT and link patients with follow-up care for their OAUD. Hospitalization is an opportune time to initiate MAT and provide linkage to follow-up care for patients with either an OUD or AUD.¹⁶ To our knowledge, no experimental studies have focused on initiating MAT and providing focused discharge planning and follow-up monitoring for hospitalized patients with either an AUD or OUD.
- The study offers a new model—a consultation-liaison service-based START—for improving care processes for hospitalized patients with OAUDs. Hospitals have extensive experience using care managers to improve in-hospital and follow-up care for several patient populations at high risk of readmission,^{46,47} including acute medical patients,⁴⁸ and many have a consultation-liaison service to support the medical team with patients in need of behavioral health care. However, to our knowledge, there are no experimental studies of care management strategies in general or collaborative care models to improve outcomes for inpatients with OAUDs. Further, leveraging the existing consultation-liaison service is an innovative and generalizable approach to managing the large number of hospital inpatients with untreated OAUDs without burdening inpatient physicians and unit case managers who may not have the expertise or time to prescribe medications or resolve barriers to OAUD-focused discharge and follow-up. The consultation-liaison service-based START is a novel, comprehensive program for facilitating MAT initiation in the hospital and linking patients to follow-up care for two of the most common SUDs among inpatients.
- This study will provide several types of new knowledge:
 - (1) Whether a START compared with usual care improves care for hospitalized patients with an OAUD. That is, whether START leads to improved initiation of medication and linkage to follow-up care for patients who are admitted to the hospital, either for a problem related to their OAUD or for another medical issue.
 - (2) Whether a START compared with usual care reduces substance use.
 - (3) Whether a START is feasible and acceptable with in the inpatient medical setting. These knowledge gains will provide invaluable, preliminary information on how to improve the quality of care for hospitalized patients with OAUD and on how to address an unmet need that has severe individual and societal consequences. The knowledge obtained in the study (and even more so in the larger, subsequent RCT) not only will benefit individual patients who participate in the study but also hospitals looking for a pragmatic and feasible way to improve OAUD care. On a societal level, providing a new way to identify and initiate treatment for patients with OAUD could fill a previous unmet need and bring down healthcare costs related to untreated OAUD. We believe that the long-term gains of the study, in terms of knowledge and substantive gains to the community, far exceed any risks for participants.

Table 2: Flowchart of Procedures

Research Procedures	Baseline visit	During course of hospital stay	1-month post-discharge
Eligibility	R		
Informed Consent	R		
Randomization	R		
Sociodemographic Data	R		
Mental health symptoms (PHQ-9, GAD 7); pain (PEG); substance use (WHO ASSIST, NSDUH) consequences of use (SIP-AD), service utilization (NSDUH, GAIN), stigma (SASS)	R		R
Satisfaction with START intervention ^a			R
Medication for alcohol or opioid use disorder ^b		S	
Therapy for alcohol or opioid use disorder ^b		S	
START Addiction Medicine Specialist (AMS) coordinates team-based care ^c		R	R
START Care Manager (CM) ^c coordinates team-based care		R	R

LEGEND

R = Research item/procedure done only for research purposes and covered by the study

S = Standard of care item/procedure that is part of regular care and billed to the patient/insurance

Footnotes:

- a. Only for patients randomized to the START intervention arm of the study.
- b. For both groups: Usual Care and Start intervention. Includes Brief Negotiated Interview and addiction focused discharge planning and follow-up.
- c. The START intervention utilizes established standard-of-care services and procedures (care manager, addiction medicine specialist, medication treatment, therapy, etc.) and helps integrate them into the patient's care in a systematic way. It is this planned coordination and integration that are the intervention, not the services themselves.

- A list of written materials that will be part of the research is included in Appendices - section 8.0 below.

Behavioral Intervention

The START Manual with a full description of the behavioral intervention is provided in a separate document.

Surveys

- Survey methodology – Patient baseline surveys will be conducted in person or remotely by the approved study staff and responses entered directly into the REDCap database using a mobile device or computer. Patient follow-up surveys will be conducted by the approved study staff via telephone.
- Survey selection – validated surveys that are most relevant to the primary and secondary study outcomes and covariates.
- Surveys are available only in English – only subjects fluent in English will be enrolled.
- Surveys used are validated as listed in Table 2: Flowchart of Procedures.

5.0 DATA COLLECTION AND MANAGEMENT

5.1 DATA PROCUREMENT

- Recruitment information will be procured through physician referral, or through review of an existing daily EPIC workbench report* of opioid and alcohol misuse.
- Administrative outcomes will be procured through a monthly EPIC report.**
- Patient Baseline Survey Measures will be procured through patient interviews and will be recorded on a tablet or computer into a web-based survey system (REDCap).
- Some demographic and all diagnosis variables will be procured from eligibility screener conducted in REDCap. (Eligibility screener variables from all patients that screen will be used to assess study feasibility. Data from patients not enrolled in the study will be anonymous, i.e., they will not be linked to an MRN or any identifying information.)
- Patient Follow-up Survey Measures will be procured through a telephone interview by 1-month after the patient is discharged from the hospital. During collection of contact information at the baseline visit, patients may opt-in to receive text message reminders about this interview. These reminders will be sent via Twilio SMS through REDCap and will not contain any identifying information regarding the patient or the specific study.
- Provider Survey Measures will be procured through provider interviews and will be recorded and transcribed.

5.2 TIME PERIOD OF DATA UNDER REVIEW

- Data will be collected prospectively at the following timepoints: Baseline interview (patient); 1-month follow-up interview (patient); Follow-up interview (providers) to be collected post-intervention, in the 3-4 months after the last patient has completed the study.

- Consent forms will be retained at CSMC for seven years after completion of the study. Linking files and identifiable information will be destroyed within a year after study completion. A limited data set will be retained for five years after study completion to allow ample time for analysis and publication.

5.3 VARIABLES COLLECTED

- The following data points/variables will be collected:

Baseline Measures:

Variable	Source Document
Demographics 
 • Age • Sex (Biological at Birth) • Gender (Identity) • Race/ethnicity • Housing status • Marital status • Income • Education 	Demographics Form
Mental Health Symptoms 
 • Depression • Anxiety 	PHQ-9 survey ^{51,52} GAD 7 survey ⁵³⁻⁵⁵
Pain intensity and frequency	PEG ⁵⁶
Alcohol/Opioid Diagnosis	WHO ASSIST ⁵⁷
30-day Alcohol/Opioid Use: National Survey on Drug Use and Health 30-day use questions	Patient Survey (Adapted from NSDUH ⁵⁸)
SUD Treatment Utilization	Patient Survey (Adapted from NSDUH ⁵⁸)
Healthcare Utilization Related to SUD	Patient survey (Adapted from GAIN ⁵⁹)
Employment	Patient Survey
Negative Consequences	Short Inventory of Problems Alcohol and Drugs (SIP-AD) ⁶⁰
Patient Experience of Stigma	Adapted from Grosso et al. 2019. ⁶¹ Questions to assess stigma experience.
Self- Stigma	Substance Abuse Stigma Scale (SASS) ⁶²
Receipt of START Intervention Components (Patient)	
START Intervention Received (Assessment, Engagement, Treatment/Discharge Planning); Length of Intervention (hours)	START Patient Registry
START Intervention Follow Up Received (Number of follow up calls made)	START Patient Registry

Follow-up Survey Measures (Patient)	
Mental Health Symptoms 
 Anxiety Depression 	PHQ-9 Survey ^{51,52} GAD 7 Survey ⁵³⁻⁵⁵
30-day Alcohol/Opioid Use: National Survey on Drug Use and Health 30-day use questions	Patient Survey (Adapted from NSDUH ⁵⁸)
SUD Treatment Utilization	Patient Survey (Adapted from NSDUH ⁵⁸)
Healthcare Utilization Related to SUD	Patient survey (Adapted from GAIN ⁵⁹)
Negative Consequences	Short Inventory of Problems Alcohol and Drugs (SIP-AD) ⁶⁰
Employment	Patient Survey
Patient Experience of Chronic Illness Care	PACIC ⁶³
Satisfaction with START intervention	Patient Survey
Provider Interviews (Provider)	
Acceptability/feasibility of START Intervention (Provider Interview Guide)	Provider Interview Guide

Outcome Measures:

Outcome	Measure, Assessment (Type of Variable)	Data Source
Primary Outcomes		
In-hospital MAT initiation	Received an OAUD MAT between admission and discharge (Binary)	CSMC admin data
Linkage to follow-up care	Received at least one visit post-discharge for MAT and/or psychosocial care for OAUD (Binary)	Appointment dates 1-month interview
Past 30-day frequency of heavy drinking days and/or all days of any opioid use	Days of use in the past 30 – Adapted National Survey of Drug Use and Health (NSDUH) ⁵⁸ (Continuous)	Baseline interview 1-month interview
Secondary Exploratory Outcome		
90-day readmission to CSMC	Readmitted to CSMC up to 90-days after discharge during study period	CSMC admin data
Covariates		
Sociodemographics	Gender, sex, age, race/ethnicity, income, education, occupational status, marital status, zip code, homelessness in past six months.	Eligibility screener; Baseline interview
OAUD diagnosis	Moderate or Severe, ASSIST ⁴⁵	Eligibility screener
Pain Level	Pain level between 1-10; Pain interference level between 1-10, PEG ⁵⁶ (Continuous)	Baseline interview 1-month interview
Primary and secondary diagnosis (inpatient stay)	Medical or mental health conditions as determined by the inpatient physician (Categorical)	CSMC admin data
Length of hospital stay	Number of days of hospital stay (Continuous)	CSMC admin data
Intervention “dose”; exposure	Amount time spent with patient (Continuous)	START Registry
Insurance	Payer name	CSMC admin data

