****Monthly EPIC Report Elements**

- Demographics: MRN; Age; Age at encounter; Date of Birth; Sex; Race; Ethnicity; City; Zip Code
- Hospital encounter data: Type; Dates; Disposition; Attending provider; PCP; Psychiatry consult;
- Diagnoses during encounter: ICD 10s: F10-F19; Problem list items
- CIWA Protocol and measure information
- Inpatient and discharge medication information: Suboxone; Buprenorphine; Subutex; Methadone; Naltrexone; Naloxone; Disulfiram; Acamprosate; Topiramate; Gabapentin; Narcan; Naloxone.
- Lab results: AST; ALT; GGT; Urine Toxicology Screen; Blood Alcohol Level
- Flowsheet Data: RN Alcohol Screening Questions
- Social History: Tobacco usage; Alcohol usage; Drug usage
- Family history of substance use disorder
- Notes: Physician, Nursing and Allied health Professional documentation
- Hospital Utilization Metrics: Length of Stay; Inpatient admissions in prior 12 months; ED admissions in prior 12 months; Number of 30-day readmissions

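### The window for the primary outcome of in-hospital MAT initiation opens at admission, before randomization, so MAT first given before allocation would score as an outcome

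*Combined protocol and SAP*

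**What the plan says.** The outcome table in section 5.3 names in-hospital MAT initiation as a primary outcome, taken from hospital administrative data, and measures it as "Received an OAUD MAT between admission and discharge (Binary".

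On timing, the first inclusion criterion (section 3.2) is "Inpatient at CSMC", so every candidate has been admitted before screening. Section 3.5 then has study staff "contact the attending physician, briefly explain the study, and ask the physician for permission to contact the patient", after which the medical team introduces the study. Section 4.0 states that "following consent and the baseline interview, the CSMC approved study staff will randomize the patient to the START or UC arm using REDCap".

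On prior medication, exclusion 1 (section 3.3) reads "Currently receiving FDA-approved medication treatment for an opioid or alcohol use disorder". It gives no reference time for *currently* and asks for no re-check at randomization. Table 2 places eligibility, consent and randomization together at the baseline visit.

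On analysis, section 7.1 plans logistic regression for binary outcomes, with the baseline value of the outcome as a covariate where appropriate. It names the variance of the treatment effect estimator, for use in planning a later study, among the pilot's primary goals. No baseline variable for MAT received between admission and randomization is defined.

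**The concern.** The outcome is labelled as initiation, but what is measured is receipt at any time in the stay. Allocation comes partway through the stay, and nothing in the plan limits counting to the time after it. A randomized patient who had MAT earlier in the stay is therefore a success by definition, whichever arm is drawn.

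At stake are the usual-care rate, the effect estimate and its standard error. The pilot disclaims power, so a lost significance test is not the issue. Planning inputs for the later trial are among its stated products, and these would describe a mixture of START's effect and events that precede it.

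**Working it through.** **Nothing to reproduce.** The plan gives no MAT rate, effect size or power for this outcome. The sample size of 80 is 2 × 40, which agrees with 16 per month × 5 months (section 7.2). It does not depend on the outcome definition.

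**Who could carry MAT from before allocation.** Setting section 5.3 beside sections 3.3 and 4.0 and Table 2 leaves three routes:

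1. MAT given and stopped earlier in the stay, so that the patient is not receiving it at screening.
2. MAT started between screening and randomization. Table 2 and the 30–40 minute interview suggest that this interval is short.
3. Patients enrolled while on MAT begun in the stay, if *currently* is read as meaning before admission.

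Let p be the share of randomized patients who enter by these routes. The documents do not give p.

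**Formulas.** Let r₀ and r₁ be the true post-randomization rates in usual care and START among the other patients.

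- Observed rate in an arm = p + (1 − p)r. The increment is p(1 − r), which is larger in the arm with the lower rate.
- Observed risk difference = (1 − p)(r₁ − r₀).

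**Illustration** with assumed r₀ = 10% and r₁ = 40%:

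| p | Expected patients of 80 | UC rate | START rate | Risk difference | Odds ratio |
|---|---|---|---|---|---|
| 0 | 0 | 10.0% | 40.0% | 30.0 points | 6.0 |
| 2% | 1.6 | 11.8% | 41.2% | 29.4 points | 5.2 |
| 5% | 4 | 14.5% | 43.0% | 28.5 points | 4.4 |
| 10% | 8 | 19.0% | 46.0% | 27.0 points | 3.6 |

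At p = 5%, for example, the odds ratio is (0.430/0.570)/(0.145/0.855) = 4.4.

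**Chance imbalance.** Randomization makes p equal across arms only in expectation. With 40 per arm, the standard deviation of the difference in pre-allocation counts is √(2 × 40 × p(1 − p)): 1.3 patients at p = 2%, 1.9 at 5% and 2.7 at 10%.

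**Consequence for planning**, with a second assumed pair of 20% and 40%. The n per arm for a later trial (two-sided 5%, 80% power, normal approximation) goes from 82 at p = 0 to 87 at 2%, 96 at 5% and 112 at 10%. Between p = 0 and p = 10%, with 40 per arm, the standard error of the risk difference rises from 0.100 to 0.106, while that of the log odds ratio falls from 0.510 to 0.474. The variance estimate can therefore move either way, depending on the scale.

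**What a later start to the window restores.** Suppose patients with earlier MAT are scored as non-initiators. The arm rates become (1 − p)r. With 10% and 40% and p = 10%, these are 9% and 36%, and the odds ratio is (0.36/0.64)/(0.09/0.91) = 5.7 instead of 3.6. The risk difference over all randomized patients is still 27 points, because those patients have no initiation left to make. Only among patients without earlier MAT, a group defined before allocation, does it return to 30 points.

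**The case against.** The strongest reply is that the gap is already nearly closed. Exclusion 1, read at face value at screening, removes anyone started on MAT in the stay and still taking it. Eligibility, consent and randomization share one visit, so little can happen between screening and allocation. Section 1.0 says that these drugs are seldom given in hospitals. A pre-allocation share of 10% would equal the whole usual-care rate assumed above, which is hard to credit. The risk difference has a standard error of √(0.1 × 0.9/40 + 0.4 × 0.6/40) = 9.1 points with 40 per arm, so a shift of 0.6 to 1.5 points (p = 2% to 5%) is lost in random error. All of this stands as to size. It does not show that the definition is right: the exclusion has no stated reference time and no re-check, and the outcome still scores events from before allocation.

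A reader might infer three stronger things that the documents do not support.

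- **That dilution is established.** It is not: p is unknown and may be near zero.
- **That one arm is favoured.** Pre-allocation receipt cannot depend on allocation. What results is attenuation plus chance imbalance.
- **That gabapentin, topiramate or naloxone would be scored as initiation because the monthly EPIC report extracts them.** That report is a general extract ("Inpatient and discharge medication information: Suboxone; Buprenorphine; Subutex; Methadone; Naltrexone; Naloxone; Disulfiram; Acamprosate; Topiramate; Gabapentin; Narcan; Naloxone", alongside laboratory results and notes), and the outcome requires an OAUD MAT. Which drugs qualify is a separate missing detail. The idea that the recruitment call prompts orders before allocation is likewise conjecture.

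**Conclusion.** The point holds as a defect of definition whose size is unknown and probably small. The outcome window opens before randomization, and no rule confines counting to the time after it. Exclusion 1 and the single baseline visit leave a residual share p through the three routes listed. The risk difference shrinks by exactly (1 − p). Under assumed rates of 10% and 40%, the odds ratio falls from 6.0 to about 5.2, 4.4 or 3.6 at p = 2%, 5% or 10%; at p near zero nothing changes. The rates and all values of p are assumptions. The calculation also takes p as equal across arms in expectation, and the later effect in the remaining patients as unrelated to p. The consequence falls on the effect and variance estimates handed to the later trial, since the pilot claims no power of its own.

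**What to change.** In section 5.3, define the outcome as an OAUD MAT first started after the randomization date and time and received by discharge. State that a drug begun earlier in the same stay and continued after randomization is not an initiation. Add MAT received between admission and randomization as a baseline variable and report it by arm. That variable also allows the result to be shown in patients without earlier MAT, where the (1 − p) factor disappears. The rule works under either reading of *currently* in exclusion 1.

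Ask for medication dates and times in the EPIC extract. The monthly report elements list inpatient and discharge medication information but do not mention timing.

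The cost is a few sentences in section 5.3 and a more specific data request, with no new patient procedures. Observed rates in both arms may be slightly lower.
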